10.2.5 Cough

Cough as an isolated symptom will be reported as an AE in the e-CRF. For cough associated with a defined clinical entity (e.g., upper respiratory tract infection), the appropriate diagnosis associated with the cough will be recorded in the AE e-CRF.

10.3 OBLIGATION OF THE INVESTIGATOR REGARDING SAFETY REPORTING**10.3.1 General guidelines for reporting adverse events**

All AEs, regardless of seriousness or relationship to IMP/NIMP, occurring between consent/assent and the end of the study will be recorded.

AEs are to be recorded as defined by the protocol on the corresponding e-CRF for subjects who are enrolled and for those who fail screening.

For screen failed subjects, recording in the e-CRF is only performed in case of an SAE occurring during the screening period or in case of an AE when some study-specific screening procedures expose the subject to safety risks. Whenever possible, diagnosis or syndrome should be reported instead of individual associated symptoms (e.g., record “Influenza” not fever, chills, etc). The Investigator should specify the date of onset, intensity (see definitions in Section 10.2.1), action taken with respect to IMP/NIMP, corrective treatment/therapy given, additional investigations performed, outcome, and Investigator’s opinion as to whether there is a reasonable possibility that the AE was caused by the IMP/NIMP.

In order to ensure the safety of the subjects, the Investigator should take appropriate measures to follow all AEs until clinical recovery is complete and laboratory results have returned to normal, or until no further improvement is expected, or until death. Follow-up of the AE resolution/status will end at the follow-up visit. If necessary, SAEs will be followed beyond the last planned visit per protocol until resolution, no further improvement is expected, or death. Additional investigations of the SAE may be requested by the Sponsor.

When treatment is prematurely discontinued, an early termination (ET) visit should be conducted as soon as possible. Laboratory, vital sign, or electrocardiogram abnormalities are to be recorded as AEs only if:

- Laboratory and/or vital signs not specifically addressed elsewhere in the protocol change $\geq 10 \times$ the upper or the lower limits of normal and are undesired, and are a change from the pre-enrollment assessment values, and/or
- Are symptomatic, and/or

- Are clinically significant

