8 STATISTICAL METHODS

8.1 General Considerations

In this study, unless otherwise specified, all analyses will be performed in a descriptive manner by age cohort (including ‘Cohort 1’, ‘Cohort 2’, ‘Cohort 3’ and ‘Total’). The ‘Total’ group will include all subjects in the analysis population.

Where appropriate, all dimensions will be summarized in metric units, but listings will, in addition, represent values as collected.

For continuous variables, the number of subjects, mean, standard deviation, median, minimum, and maximum values will be displayed, as appropriate according to the type of data. The minimum and maximum will be displayed to the same number of decimal places that the data were recorded to. The mean and median will have 1 extra decimal place and the standard deviation will have 2 extra decimal places. The geometric mean and coefficient of variation (CV) will have 2 extra decimal places. Confidence interval (of the mean) will have the same decimal precisions as the mean.

For categorical variables, frequency counts and percentages of total for each category will be presented; missing values will be treated as a separate category, where appropriate. Percentage will be presented in 1 decimal place.

Visit specific data (e.g., 7-point SMBG or pulmonary function tests) will be summarized by analysis visit, which is defined based on the visit windows specified in Section 0

Non-visit specific data (e.g., hypoglycemic events or daily dose) will be summarized by study period and/or by time interval. See relevant sections for more details.

8.1.1 **Data Handling/Imputation Methods**

8.1.1.1 **Missing Data Imputation**

Unless otherwise specified, missing data other than start date of adverse events (AE) or start/end date of concomitant medications (CM) will not be imputed.

The imputation rules for start date of Aes and start/end date of CMs are as follows:

Adverse Events

- Start date
 - If the start date is completely missing, the start date is set to the date of first dose.
 - If the year is present and the month and day are missing or the year and day are present and the month is missing:

If year = year of first dose, then set month and day to month and day of first dose

Version Date: 17-Jan-2020

- If year < year of first dose, then set month and day to December 31.
- If year > year of first dose, then set month and day to January 1st.
- If the month and year are present and the day is missing:
 - If year = year of first dose and

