8.3.5 Pulmonary Function Testing

Schedule and parameters

Spirometry tests will be performed at screening, visits 2, 9, 15, and 16 in the titration period, visits 19, 22, 25, 28, and 29 in the extension period, as well as at the early termination visits in both periods. At each visit, Forced Expiratory Volume in 1 second (FEV₁) will be collected. At Visit 2, FEV₁ will be collected at several time points: -25 min, 18 min, 55 min, 125 min and 245 min relative to the time of first dose.

Table presentation

FEV₁ value and change from baseline will be summarized descriptively by cohort and analysis visit/nominal time point. For each post-baseline visit/time point, number and percentage of subjects with verified clinically relevant decline in pulmonary function from baseline (as indicated on the eCRF) will be presented by cohort. For percentage calculations, the total number of subjects in each cohort who attend the visit will be used as denominators.

Verified clinically relevant decline in pulmonary function will be captured as AE. A continuous decline will be captured as a single AE. The start date of this event is defined as the date when the criterion of clinically relevant decline (i.e., >15% decrease from baseline) is met for the first time, and the end date of this event is defined as the date when the criterion is no longer met. Each event will be assigned to a study period based on the start date. Duration (in days) of an event will be calculated as end date – start date + 1, and summarized by cohort and study period.

Subject Listings

For spirometry tests, detailed information of every measurement will be listed, by (in the order of) cohort, investigator site, subject and visit/time point.

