Table 14.3.1.4	Treatment-emergent Adverse Events by Severity and System Organ Class/Preferred Term – Safety Population	
Table 14.3.1.5	Most Common Treatment-emergent Adverse Events Where Preferred Term Is $\geq 5\%$ – Safety Population	
Table 14.3.1.6	Treatment-emergent Serious Adverse Events by System Organ Class and Preferred Term – Safety Population	X
Table 14.3.1.7	Treatment-emergent Serious Adverse Events by Relationship to Study Drug and System Organ Class/Preferred Term – Safety Population	
Table 14.3.1.8	Treatment-emergent Adverse Events Leading to Study Discontinuation by System Organ Class and Preferred Term – Safety Population	
Table 14.3.1.9	Treatment-emergent Adverse Events Leading to Death by System Organ Class and Preferred Term – Safety Population	
Table 14.3.1.10	Treatment-emergent Adverse Events Leading to Temporary Treatment Interruption by	

	System Organ Class and Preferred Term – Safety Population	
Table 14.3.1.11	Treatment-emergent Adverse Events of Special Interest by System Organ Class/Preferred Term – Safety Population	
Table 14.3.1.12	Treatment-emergent Adverse Events of Special Interest by Relationship to Study Drug and System Organ Class/Preferred Term – Safety Population	
Table 14.3.2.1	Summary of Hypoglycemic Events – Safety Population	X
Table 14.3.2.2	Summary of Causality of Hypoglycemic Events – Safety Population	
Table 14.3.3.1	Value and Change from Baseline in Vital Signs – Safety Population	X
Table 14.3.4.1	Value and Change from Baseline in FEV ₁ – Safety Population	X
Table 14.3.4.2	Summary of Clinically Relevant Decline from Baseline in Pulmonary Function – Safety Population	X
Table 14.3.4.3	Summary of Duration of Verified Clinically Relevant Decline from Baseline in Pulmonary Function– Safety Population	
Table 14.3.5.1	Shift Table for Anti-insulin Antibody – Safety Population	X
Other		
Table 14.4.1.1	Value and Change from Baseline in HbA1c (%) – Safety Population	
Table 14.4.2.1	Average of Value and Change from Baseline in Fasting pre-breakfast SMBG (mg/dL) (eDiary Data) – Safety Population	
Table 14.4.3.1	Average of Value and Change from Baseline in Post-prandial SMBG (mg/dL) by Meal (eDiary Data) – Safety Population	
Table 14.4.4.1	Summary of 7-Point SMBG (mg/dL) by Time Point and Visit (eDiary Data) – Safety Population	
Table 14.4.4.2	Value and Change from Baseline in Mean of 7-Point SMBG (mg/dL) (eDiary Data) – Safety Population	

List of Listings		Include in DMC
Patient Disposition		

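### The duration table for clinically relevant FEV1 decline has no rule for declines still present at the last spirometry, so as written it summarises resolved declines only

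*SAP*

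**What the plan says.** SAP 8.3.5 treats verified clinically relevant decline in pulmonary function as an adverse event: "A continuous decline will be captured as a single AE". The event starts on "the date when the criterion of clinically relevant decline (i.e., >15% decrease from baseline) is met for the first time". For its close, "the end date of this event is defined as the date when the criterion is no longer met". The summary measure follows: "Duration (in days) of an event will be calculated as end date – start date + 1, and summarized by cohort and study period". The planned output is Table 14.3.4.3 in SAP Appendix 3, "Summary of Duration of Verified Clinically Relevant Decline from Baseline in Pulmonary Function".

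Three other provisions decide what happens to a decline that does not resolve:

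- **Missing dates.** SAP 8.1.1.1 states that, unless otherwise specified, "missing data other than start date of adverse events (AE) or start/end date of concomitant medications (CM) will not be imputed". Adverse event end dates are not among the exceptions.
- **End of observation.** Protocol 10.3.1 states: "Follow-up of the AE resolution/status will end at the follow-up visit". The sentence after it allows serious adverse events to be followed further if necessary.
- **When FEV1 is measured.** Besides screening and early termination, SAP 8.3.5 schedules spirometry at "visits 2, 9, 15, and 16 in the titration period, visits 19, 22, 25, 28, and 29 in the extension period".

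SAP 8.3.1 lists not recovered or resolved among the adverse event outcomes, so the plan expects that some events will be open at the end. SAP 8.3.5 gives no censoring date, no category for ongoing declines and no time-to-resolution method.

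**The concern.** Clinically relevant decline in pulmonary function is an adverse event of special interest (Protocol 10.2.3, SAP 4.2). The SAP's revision history explains that the duration table was added because the length of such declines matters. For an inhaled product in children, the practical question behind a duration is whether the loss reverses. A table that can hold only the declines that reversed cannot answer it, and its mean or median may be read as describing all declines.

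Open declines are easy to foresee. A decline first seen at the last scheduled spirometry has no later scheduled test. After early termination, Protocol 12.1.4 provides a telephone contact within 3 days and no further spirometry. According to Protocol 4.2, the study helps set the age range and dosing for a 1-year paediatric trial, so its lung findings will be used.

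Protocol 4.4 reports that an FEV1 difference in adults lasted throughout observed treatment, up to 2 years. That is a mean difference of 40 mL, not an individual fall of more than 15%. It makes persistence a fair question but does not predict how often it will occur here.

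**Working it through.** The plan states no figure for the duration of decline, so there is nothing to reproduce. The check applies the SAP rule to the SAP's own schedule.

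**1. Inputs.** Titration spirometry falls at target Days 1, 15, 29 and 36 (Protocol 1.1). With the SAP's extension, which starts the day after Visit 15 (Day 30), the targets in SAP Table 2 are start day + 91, 183, 274, 365 and 396, that is Days 121, 213, 304, 395 and 426. Duration = end date − start date + 1.

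**2. Durations at target days, titration only**

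| First seen | Resolved by (duration in days) | Still present on Day 36 |
|---|---|---|
| Day 1 | same day (1), Day 15 (15), Day 29 (29), Day 36 (36) | no value; true length at least 36 |
| Day 15 | Day 29 (15), Day 36 (22) | no value; at least 22 |
| Day 29 | Day 36 (8) | no value; at least 8 |
| Day 36 | none | no value |

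The 1-day entry arises because Visit 2 has four post-dose tests. Visit windows (±1 day, ±3 days for Visit 16) and early-termination visits shift these values. Extension visits give a child still down at Visit 15 later chances to resolve. The last column keeps the same form: a decline present from Day 29 through Day 426 has lasted at least 426 − 29 + 1 = 398 days and contributes nothing.

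**3. Illustration (assumed counts).** Five declines are first seen on Day 15; two have resolved by Day 29 and three are present on Day 36.

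- SAP rule: n = 2, mean (15 + 15)/2 = 15.0 days.
- Ongoing declines at their minimum of 36 − 15 + 1 = 22 days: mean at least (2 × 15 + 3 × 22)/5 = 96/5 = 19.2 days.
- Kaplan-Meier median: not reached, since 2/5 = 40% resolved.

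**4. Does the table respond to persistence?** This was simulated on the extension schedule. Assumptions: onset uniform from Day 1 to Day 395; resolving declines exponential with median 60 days; 0%, 25% or 50% of declines permanent.

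| Permanent | Detected declines with a duration | SAP mean | SAP median | Kaplan-Meier median |
|---|---|---|---|---|
| 0% | 76% | 111.7 | 93 | 93 |
| 25% | 50% | 111.9 | 93 | 183 |
| 50% | 30% | 112.3 | 93 | not reached |

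The SAP median did not move with the permanent share when the assumed median was 14 days (92 throughout) or 180 days (93 throughout). On the titration schedule it was 15 in every case. The resolved-only summary mainly reflects visit spacing.

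**5. Direction.** Understatement is not certain.

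- Suppose child A declines on Day 1 and resolves on Day 29 (29 days). Child B declines on Day 29, is still down on Day 36 and in truth recovers on Day 38 (10 days). The table reports 29; the true mean is (29 + 10)/2 = 19.5.
- Resolution is dated only at the next spirometry, so a decline seen on Day 15 that recovers on Day 17 is recorded as 15 days.

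**The case against.** The strongest reply is that little is lost. Table 14.3.4.2 gives the number and percentage with verified decline at every post-baseline visit, including follow-up. Table 14.3.4.1 shows FEV1 change by visit. The special-interest event tables and listings carry each event, SAP 8.3.1 records its outcome, and Listing 16.2.8.3 shows every spirometry value. Table 14.3.4.3 is not marked for the DMC package, whereas 14.3.4.1, 14.3.4.2 and the spirometry listing are. The table shells are separate files not available here and may contain a row for ongoing declines. The study is descriptive, with about 46 children in cohorts of 14 to 18, and may yield few such declines or none.

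Most of this stands. A reader might infer that the plan hides persistent declines from the report; it does not. The gap is confined to one derived variable. A reader might also infer that a decline first seen at Visit 16 can never gain an end date; the exception for serious events in Protocol 10.3.1 means that it might.

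Two things remain. The by-visit table is a cross-section of attendees and does not follow the same child from onset to resolution, so it does not replace a duration summary. And whatever the shells hold, the SAP text defines duration through an end date that an ongoing decline lacks. If a programmer inserted the last visit date, that would be an unspecified rule which also understates duration.

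**Conclusion.** The point holds in a limited form. Followed as written, SAP 8.3.5 with 8.1.1.1 makes Table 14.3.4.3 a summary of resolved declines, unable to show persistence. When some declines persist it will usually understate duration.

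The size cannot be derived from the documents: they give no expected number of declines of more than 15% and no resolution rate, and the effect is nil if none is unresolved. The 15.0 against 19.2 days and the simulated medians rest on assumed inputs and show the mechanism only. The stronger reading, that the bias always runs towards shorter durations, is not supported: the two-child example and the visit spacing can each push the reported figure upwards.

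The conclusion assumes that the unseen shells add no handling of ongoing declines. How much censoring to expect depends on the extension. The SAP cites Protocol Amendment 2 and includes 52 more weeks; the current protocol, Amendment 3, ends scheduled follow-up at about Day 36, which leaves less time to observe resolution.

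**What to change.** Amend SAP 8.3.5 and the shell of Table 14.3.4.3 as follows:

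1. Show, by cohort and study period, the number of declines, the number resolved and the number ongoing at the last spirometry, counting early-termination visits as last spirometry where they apply.
2. Treat an ongoing decline as right-censored at the date of the last spirometry and list it as ≥ x days, where x = last spirometry date − start date + 1.
3. Add a Kaplan-Meier time to resolution only if there are enough events to make it readable; otherwise the list suffices.
4. Do not present a mean or median of resolved declines without the ongoing count beside it.
5. Footnote that start and end are dated at spirometry visits, so recorded durations depend on visit spacing.

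The cost is SAP wording and one table shell. The dates and outcomes are already collected, so no new data are needed.

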5.4 Study Period

Two study periods are defined: an approximately 4-week titration period (Visit 2 – Visit 16, including PK assessments at Day 1) followed by an optional 52-week extension period (Visit 17 – Visit 29). Participants in the titration period are defined as subjects who take at least one dose of study drug in the titration period and participants in the extension period are defined as subjects who complete the titration period and opt to participate in the extension study.

Start date of the titration period is defined as Study Day 1. For subjects who do not participate in the extension period, end date of the titration period is defined as the last visit/contact date; for

subjects who participate in the extension period, end date of the titration period is defined as the date of Visit 15.

Start and end date of the extension period are defined for subjects who participate in the extension period only. Start date is defined as date of Visit 15 +1 day, and end date is defined as the last visit/contact date.

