8.1.1.2 Visit Window

Visit windows are defined for visit-specific parameters as following:

Table 2 Visit Window

Parameter	Study Period	Analysis Visit	Target Relative Day (s)*	Visit Window (Relative Days)*
HbA1c, Anti-insulin antibody	Screening	Screening	-21 to -7	[Day of ICF signed, - 1]
	Titration	Week 4 (Visit 15, EOT)	29	[22, 36]
	Extension	Month 12 (Visit 28, EOT)	Start day of the extension period + 365	[Start day of the extension period + 337, End day of the extension period + 393]
FEV ₁	Screening	Screening	-21 to -7	[Day of ICF signed, - 1]
	Titration	Day 1	1	No visit window, data collected on that day will be summarized by nominal time point
		Week 2 (Visit 9)	15	[8, 21]
		Week 4 (Visit 15, EOT)	29	[22, Treatment end day of the titration period]
		Follow-up	36	[Treatment end day of the titration period + 1, End day of the titration period]. Only subjects who opt not to participate in the extension period should have this visit.
	Extension	Month 3	Start day of the extension period + 91	[Start day of the extension period + 77, Start day of the extension period + 105]
		Month 6	Start day of the extension period + 183	[Start day of the extension period +169 , Start day of the extension period +197]
		Month 9	Start day of the extension	[Start day of the extension period +260, Start day of the extension period +288]

Parameter	Study Period	Analysis Visit	Target Relative Day (s)*	Visit Window (Relative Days)*
			period + 274	
		Month 12 (Visit 28, EOT)	Start day of the extension period + 365	[Start day of the extension period + 351 , Treatment end day of the extension period]
		Follow-up	Start day of the extension period + 396	[Treatment end day of the extension period +15, End day of the extension period]
Vital Signs and 7-Point SMBG	Screening	Screening	-21 to -7	[Day of ICF signed, - 1]
	Titration	Day 1	1 (for Vital Signs only)	No visit window, data collected on that day will be summarized by nominal time point
		Week 1 (Visit 5)	8	[5, 11]
		Week 2 (Visit 9)	15	[12, 18]
		Week 3 (visit 12)	22	[19, 25]
		Week 4 (Visit 15, EOT)	29	[26, Treatment end day of the titration period]
		Follow-up (for Vital Signs only)	36	[Treatment end day of the titration period +4, End day of the titration period]. Only subjects who opt not to participate in the extension period should have this visit.
	Extension	Month 3	Start day of the extension period + 91	[Start day of the extension period + 77, Start day of the extension period + 105]

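### The duration of FEV1 decline in SAP 8.3.5, summarised by study period, mostly records the gap between spirometry tests, which ranges from 7 to 92 days

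*SAP*

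**What the plan says.** Under SAP 8.3.5, a verified clinically relevant decline in pulmonary function is an adverse event. It starts on the date the criterion of more than 15% below baseline is first met, and "the end date of this event is defined as the date when the criterion is no longer met". The section continues: "Each event will be assigned to a study period based on the start date". The statistic is then fixed: "Duration (in days) of an event will be calculated as end date – start date + 1, and summarized by cohort and study period". It feeds Table 14.3.4.3 (SAP Appendix 3). SAP Section 9 gives the reason for the table: sites verify the decline, and its duration is of interest.

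The schedule is in the same section: "Spirometry tests will be performed at screening, visits 2, 9, 15, and 16 in the titration period, visits 19, 22, 25, 28, and 29". The last five of these visits belong to the extension, and early termination visits are added. SAP 8.1.1.2, Table 2, gives the target days. In titration these are Days 1, 15, 29 and 36. For the Day 36 follow-up the table adds: "Only subjects who opt not to participate in the extension period should have this visit". The first extension test is at "Start day of the extension period + 91", then at start + 183, + 274, + 365 and + 396. SAP 5.4 fixes the extension start: "Start date is defined as date of Visit 15 +1 day". For subjects who continue, titration ends on the date of Visit 15.

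SAP 8.3.5 has no rule for a decline that begins or ends between tests, for one still present at the last test, or for unequal test spacing.

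**The concern.** The true start and end of a decline fall somewhere between two tests. A duration built from test dates alone therefore carries the test spacing with it. Uniform spacing would make this a shared coarseness; here the spacing changes sharply at Visit 15, close to where the SAP divides its summary.

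Clinically relevant decline in pulmonary function is an adverse event of special interest for an inhaled insulin in children. A table of duration by period invites the reader to ask whether declines last longer with continued exposure. If the recorded number mostly reflects when the next test was due, the table cannot answer that. Event counts by period are affected too, because widely spaced tests miss more short declines.

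**Working it through.** The plan gives no figure for this quantity, so there is none to reproduce. The check applies the SAP 8.3.5 rule to the Table 2 target days.

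**Test days.** With Visit 15 on Day 29, the extension starts on Day 30.

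- Subjects not continuing: Days 1, 15, 29, 36. Gaps: 14, 14, 7.
- Subjects continuing: Days 1, 15, 29, then 30 + 91 = 121, 30 + 183 = 213, 30 + 274 = 304, 30 + 365 = 395, 30 + 396 = 426. Gaps: 14, 14, 92, 92, 91, 91, 31.

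**Recorded duration when a decline is seen at one test and gone at the next** (next test day − detecting test day + 1):

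| First seen | Assigned to | Recorded days |
|---|---|---|
| Day 15 | titration | 29 − 15 + 1 = 15 |
| Day 29, not continuing | titration | 36 − 29 + 1 = 8 |
| Day 29, continuing | titration | 121 − 29 + 1 = 93 |
| Month 3 | extension | 213 − 121 + 1 = 93 |
| Month 6 | extension | 304 − 213 + 1 = 92 |
| Month 9 | extension | 395 − 304 + 1 = 92 |
| Month 12 | extension | 426 − 395 + 1 = 32 |

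A decline first seen after dosing on Day 1 is recorded as 1 day if it clears within that day's tests, and as at least 15 days otherwise.

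**Recorded means.** Assumptions: onset is uniform over Days 1 to 29 (28 days) or Days 30 to 395 (365 days), the decline is continuous, and only scheduled tests are used. A test catches a decline of true length L if onset fell in the L days before it.

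- *Titration, not continuing, L = 7.* Caught at Day 15 (7 onset days) or Day 29 (7). Seen: 14/28 = 50%. Mean = (15 + 8)/2 = 11.5.
- *Titration, not continuing, L = 14.* All are seen. Onsets in 14 of 28 days record 15 days, and 7 of 28 record 8 days. The last 7 of 28 (25%) are still in decline at Day 36 and have no end date. Mean of the resolved = (14 × 15 + 7 × 8)/21 = 266/21 = 12.7.
- *Titration, continuing, L = 7 or 14.* Half record 15 days and half 93. Mean = 54.
- *Extension, L = 7 or 14.* Mean = (93 + 92 + 92 + 32)/4 = 77.25. Seen: 4 × 7/365 = 7.7% for 7 days and 4 × 14/365 = 15.3% for 14 days, so about 92% and 85% are never seen.

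The extension mean is the same for any true length up to 31 days, the shortest extension gap.

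**Pooled titration row.** The share of titration events from continuing subjects, p, is not given. For L = 7 the titration mean is 11.5(1 − p) + 54p:

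| p | Titration mean | Extension mean ÷ titration mean |
|---|---|---|
| 0 | 11.5 | 6.7 |
| 0.25 | 22.1 | 3.5 |
| 0.5 | 32.8 | 2.4 |
| 0.75 | 43.4 | 1.8 |
| 1 | 54 | 1.4 |

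**Visit windows.** Months 3 and 6 each allow ±14 days, so that gap alone can run from 92 − 28 = 64 to 92 + 28 = 120 days.

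**The case against.** The strongest reply is that the contrast between periods is not a clean one of two weeks against three months. This stands. A reader might infer a roughly sixfold inflation from the ratio of the test gaps. That needs every titration event to come from a subject tested at Day 36, and those subjects by definition contribute nothing to the extension row. In continuing subjects a decline first seen at Visit 15 is a titration event recorded as 93 days, and the ratio falls to about 1.4. The titration row is itself a mixture of 8, 15 and 93 days.

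It can also be said that the SAP ends the event when the criterion is no longer met, not at the next scheduled visit. Protocol 10.2.3 foresees further investigation of events of special interest, Protocol 10.3.1 requires follow-up of adverse events, and sites verify the decline. Retests between visits are therefore likely, and early termination visits add tests. This also stands, so the figures above are for scheduled tests only. But no retest interval is given. SAP 8.1.1.2 excludes data from unscheduled time points from analyses. That sentence belongs to the by-visit rules, and whether it reaches adverse event end dates is unclear.

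Finally, the analyses are descriptive, no test between periods is planned, and the table shells are separate files, so a side-by-side layout cannot be confirmed. The spirometry listing shows test dates, and decline is also tabulated per visit among attendees. This limits the seriousness, but a summary of duration should still respond to duration.

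**Conclusion.** The point holds as a defect in one descriptive safety summary. With scheduled tests only, the SAP 8.3.5 duration of a short decline is set by which test first sees it and whether the subject continues. For resolved 7- to 14-day declines the recorded mean is about 11.5 to 12.7 days in titration for subjects not continuing, about 54 days in titration for those continuing, and about 77 days in the extension. The first range leaves out the 25% of 14-day declines unresolved at Day 36. Short declines are also seen far less often in the extension, so counts by period are not comparable either.

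The documents do not support a single inflation factor between periods. It depends on the unstated share of subjects who continue and on retests of unknown frequency. The figures rest on target days, uniform onset and assumed true lengths. The extension itself appears in the SAP, which cites protocol Amendment 2; the Amendment 3 design does not describe it. No hypothesis test is affected.

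**What to change.** In SAP 8.3.5 and Table 14.3.4.3, replace the single duration with two bounds:

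- minimum = last test meeting the criterion − first test meeting it + 1;
- maximum = first later test not meeting it − last earlier test not meeting it − 1.

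Also:

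- Flag the maximum as open when no later negative test exists.
- State that unscheduled and early termination spirometry count towards the bounds, whatever SAP 8.1.1.2 says for by-visit summaries.
- Handle Day 1 separately. If the earlier negative test is the pre-dose test that day, the maximum is one day short. If the decline also clears that day, the formula gives 1 − 1 − 1 = −1, and both bounds should be 1 day.
- Footnote the test spacing, and say that durations and counts are not a comparison between periods.

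Counting consecutive scheduled tests in decline is not a substitute, because one test stands for about two weeks before Visit 15 and about three months after it.

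The cost is SAP wording, one table shell, and two columns instead of one. No new data are needed. The bounds will be wide in the extension: a decline seen only at Month 6 gets 1 to 304 − 121 − 1 = 182 days, against 1 to 29 − 1 − 1 = 27 days for one seen only at Day 15. The bounds show this uncertainty but do not remove it, and they do not recover declines that fell between tests.
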